3.4 Secondary endpoints/outcomes

1. Hospitalisation for COVID-19
2. Length of stay in hospital
3. Length of stay on ICU
4. Number of ventilator-free days (VFDs)
5. Length of extracorporeal membrane oxygenation (ECMO)
6. Need for kidney replacement therapy
7. Measurement of total comorbidity burden using the Charlson Comorbidity Index (CCI) and age-adjusted CCI (ACCI)
8. Estimate risk of 30-day mortality after COVID-19 infection using pre-COVID health status (estimated using the Veterans Health Administration COVID-19 (VACO) index)
9. Inflammatory marker and blood cell counts at COVID-19 diagnosis

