6.2 Data collection

Only real-world retrospective data will be used for this study. Deidentified retrospective data will be transcribed into the eCRF system from source data at each clinical site or from existing COVID-19 cohort databases, where appropriate. No personal identifiable data will be transmitted to NEAT ID. The data elements will be transcribed from source data according to the data collection list below. Mechanisms to ensure data quality and integrity will be deployed as per applicable standard operating procedures and in line with GCP and GPP. Patients and controls will be identified and documented by participating sites, provided unbiased matching for inpatient/outpatient status at the time of COVID-19 diagnosis is ensured. Alternatively, and to avoid potential site-related bias during selection of HIV negative controls with COVID-19 diagnosed in hospital, data from matched controls will be obtained from appropriate existing COVID-19 cohort databases, e.g. LEOSS (Lean European Open Survey on SARS-CoV-2 infected patients) or ISARIC (International Severe Acute Respiratory and emerging Infection Consortium).

For all patients the following information will be collected:

- Age
- Sex
- Ethnicity (where available)
- Comorbidities (see appendix 1)
- Weight (kg) and height (m) (to calculate BMI)

For patients with COVID-19 the following information will be collected (where applicable):

- Date of positive PCR test result (documented or patient-reported)
- COVID-19 diagnosis inpatient or outpatient
- All-cause mortality in hospital, or palliative discharge, or mortality at 6 weeks after diagnosis of COVID-19 or at discharge from hospital
- Hospitalisation for COVID-19 and length of hospitalisation
- Critical care admission (high dependency unit or intensive care unit) for COVID-19 and length of stay in critical care
- Length of invasive ventilation
- Length of extracorporeal membrane oxygenation (ECMO)
- Need for kidney replacement therapy
- Inflammatory markers and blood cell counts at COVID-19 diagnosis¹ (if available):
 - Full blood cell count (Platelet count, RBC Count, WBC count (absolute), Haemoglobin, Haematocrit, MCV, MCH, Neutrophils, Lymphocytes, Monocytes, Eosinophils, and Basophils), ALT, AST, total bilirubin, urea, serum creatinine, calcium, glucose and HbA1C levels, total cholesterol, triglycerides, CRP, D-dimer, ferritin, and lactate dehydrogenase

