- Drug treatment for COVID-19 (glucocorticoids, azithromycin, remdesivir, monoclonal antibodies against SARS-CoV2, convalescent plasma, anti-IL1 inhibitors, anti-IL6 inhibitors, lopinavir/ritonavir, and others)

For PLWHIV the following information will be collected:

- Date of HIV diagnosis
- Current ART
- CDC disease stage
- CD4 cell nadir
- Last CD4 cell count (including CD4% and CD4/CD8 ratio) and HIV-RNA before COVID-19 diagnosis, or most recent for HIV-only controls

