7 STATISTICS AND DATA ANALYSIS

7.1 Sample size calculation

The US Veterans Ageing Cohort Study (VACS) reported at AIDS 2020 [20] that the estimated proportion of non-HIV-infected individuals hospitalized with COVID-19 was 35%, 15% in ICU, 8% with invasive mechanical ventilation and 11% died. We anticipate a 1.1 to 2-fold increase in hazard rate in PLWHIV & COVID-19 (cases) relative to HIV-negative & COVID-19 (controls). With 500 cases and 1500 controls, a two-sided log-rank test at an alpha level of 0.05 will achieve at least 80% power to detect a 1.3-fold increase in the hazard rate of hospitalization, 1.4 for ICU, 1.6 for invasive mechanical ventilation and 1.5 for death (refer to Table 1 below). The power calculation was made using the statistical software package nQuery Advanced, with the two samples Log-Rank test module (Version 8.6.1.0).

Table 1

¹ Most recent available after positive SARS-CoV-2 PCR test, up to 10 days after positive test

		Cases (PLWHIV & COVID-19, N=500); Controls (HIV-negative & COVID-19, N=up to 1500) Alpha=5% (two-sided)										
Severity outcome	Outcome (%)	Power (%)										
Hazard Risk		1.1	1.2	1.3	1.4	1.5	1.6	1.7	1.8	1.9	2.0	
Hospitalization	35	20	60	90	99	>99	>99	>99	>99	>99	>99	
ICU	15	11	31	58	81	94	99	>99	>99	>99	>99	
Invasive mechanical ventilation	8	8	19	35	54	73	86	94	98	99	>99	
Death	11	9	24	46	68	85	95	98	>99	>99	>99	

For the search for factors associated with SARS-CoV-2 infection in PLWHIV, the recommended rule of thumb for sample size estimation for multivariable logistic regression models was $n = 100 + 50i$ where i refers to number of independent variables in the final model [34]. With 1500 PLWHIV (500 with COVID-19 and 1500 controls without COVID-19), we would be able to study 28 parameters with sufficient power to produce statistics that are nearly representative of the true values in the targeted population. However, sample size less than 1500 may be sufficient for associations that yield medium to large effect size.

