7.3.2 Primary outcome analysis

The first primary outcome analysis will be performed on PLWHIV with COVID-19 versus HIV uninfected individuals with COVID-19. The endpoint is the occurrence of critical care admission (high dependency unit or intensive care unit), mortality in hospital or palliative discharge when discharged from hospital, or mortality at 6 weeks after diagnosis of COVID-19 or at discharge from hospital (where applicable). Kaplan-Meier estimates will be used to estimate the proportion of participants with the primary endpoint events. Unadjusted and adjusted hazard ratios (HR) will be estimated using the Cox proportional hazard model to assess the impact of HIV-infection on the severity of COVID-19. The validity of the proportionality assumption will be assessed and tested. The adjusted variables will be the following (potential confounders): Age (<60 vs 60-64 vs 65-69 vs 70-74 vs ≥75 years); Sex at birth (female vs male); Obesity (BMI>30 kg/m²); and Comorbidities (see appendix 1).

The second primary outcome analysis will be performed within the group of PLWHIV (PLWHIV with COVID-19 versus PLWHIV without COVID-19). The endpoint is to assess factors associated with severe COVID-19 within the group of PLWHIV. Conditional logistic regression models will be used to account for the case-control matching. The following variables will be assessed: Age (<60 vs 60-64 vs 65-69 vs 70-74 vs ≥75 years); Sex at birth (female vs male); Obesity (BMI >30 kg/m²); Comorbidities (see appendix 1); time since HIV diagnosis (years); current ART; CDC disease stage; CD4 cell nadir; last CD4 cell count/HIV-RNA before COVID-19 diagnosis (including CD4% and CD4/CD8 ratio) at baseline. For continuous variables, the decision to treat the variable as a continuous or categorical variable (as tertile) will be based on the lowest Akaike information criterion value for the corresponding univariable conditional logistic regression analysis. Variables achieving P < 0.20 in the univariable analysis will be retained for the multivariable analysis.

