7.3.3 Secondary outcome analysis

All secondary outcome analysis will be performed on PLWHIV with COVID-19 compared to HIV uninfected individuals with COVID-19.

The proportion of hospitalised patients for COVID-19, the length of stay in hospital, the length of stay on ICU, the length of extracorporeal membrane oxygenation (ECMO), and the proportion of participants with a need for kidney replacement therapy will be estimated using the Kaplan-Meier estimate. Unadjusted and adjusted hazard ratios (HR) will be estimated using the Cox proportional hazard model to assess the impact of HIV-infection on the severity of COVID-19. The adjusted variables will be the same as those used for the first primary outcome analysis.

The number of ventilator-free days (VFDs) will be compared between groups using competing risk regression, with extubation and mortality a competing event, adjusted for potential confounders.

Linear regression models will be used to compare Charlson Comorbidity Index (CCI), the age-adjusted CCI (ACCI), 30-day mortality index after COVID infection, inflammatory marker and blood cell counts at COVID-19 diagnosis between the 2 groups, adjusted for potential confounders. The sample size will be quite large to consider CCI, 30-day mortality index, inflammatory marker and blood cell counts as normally distributed variables.

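### Secondary endpoint 9 is labelled as a value at diagnosis, but its footnote, read literally, takes the latest result in the 10 days after the positive test

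*Combined protocol and SAP*

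**What the plan says.** Section 3.4 lists secondary endpoint 9 as "Inflammatory marker and blood cell counts at COVID-19 diagnosis". Section 6.2 collects the item under the same label, "Inflammatory markers and blood cell counts at COVID-19 diagnosis", if available, with footnote marker 1. The footnote text, which prints beside Table 1 in section 7.1, is the only operational definition: "Most recent available after positive SARS-CoV-2 PCR test, up to 10 days after positive test".

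Section 7.3.3 uses linear regression to compare "inflammatory marker and blood cell counts at COVID-19 diagnosis between the 2 groups, adjusted for potential confounders". It gives no separate covariate list for the markers. The list of potential confounders is in section 7.3.2, which begins "The adjusted variables will be the following (potential confounders): Age (<60 vs 60-64 vs 65-69 vs 70-74 vs ≥75 years" and continues with sex at birth, obesity and comorbidities.

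Two related items in section 6.2 bear on timing. The date anchor is "Date of positive PCR test result (documented or patient-reported" (the bracket closes there), and no laboratory sample date is listed. COVID-19 therapy is collected as "Drug treatment for COVID-19 (glucocorticoids, azithromycin, remdesivir, monoclonal antibodies against SARS-CoV2" and further agents, without start dates.

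**The concern.** The label promises a value that describes the patient when COVID-19 was diagnosed. The footnote, taken at its word, prefers later results to earlier ones. Where samples are repeated, the recorded value may follow several days of illness and possibly the start of glucocorticoids or anti-IL6 agents, both of which are on the collected drug list. It is then partly an outcome of the disease course, although it would be reported as a feature at presentation.

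Secondary objective 4 (section 3.2) compares severity between PLWHIV and controls at diagnosis and at admission. A reader would naturally use the marker comparison for that purpose. If repeated sampling, length of stay or treatment differed between the groups, a difference in markers might not be a difference at diagnosis. Without sample dates or treatment start dates in the collection list, the analyst could not check this afterwards.

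**Working it through.** No sample size, power or alpha figure in the plan depends on this definition, so there is no stated figure to reproduce. The check is mainly of the wording.

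**1. What the rule selects.** Let a patient's results in the window fall on days d1 ≤ … ≤ dk after the positive test, each between 0 and 10.
- The label calls for the result nearest day 0, which is d1.
- The footnote, read literally, takes dk.
- The discrepancy is dk − d1. It is 0 when k = 1 and at most 10 − 0 = 10 days.
- Since d1 ≤ dk always, the earliest value is never further from diagnosis than the latest.
- Both rules need only one result in the window, so the same patients have a value under either. If the footnote's *after* is read as excluding the test day, a rule of on or after can only add patients.

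**2. Whether the text elsewhere corrects it.** Sections 3.4, 6.2 and 7.3.3 repeat the label, and none says first or closest. In the HIV data list of section 6.2, CD4 count and HIV-RNA are the last before COVID-19 diagnosis, or the *most recent* for HIV-only controls. There the phrase plainly means latest. Looking back from diagnosis, the latest value is the closest to it. Looking forward from diagnosis, the latest is the furthest away.

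**3. Whether the analysis repairs it.** The covariates in section 7.3.2 are age, sex, obesity and comorbidities. Neither sampling day nor prior COVID-19 treatment is among them, and the dates needed for either are not collected.

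**4. Size.** The documents give no marker SDs and no sampling days, so no bias can be computed. The following shows only how sensitive the comparison would be. It *assumes* complete data in 500 cases and 1,500 controls, and a shift δ between group means caused by timing alone.
- SE = SD × √(1/500 + 1/1500) = 0.052 SD
- Two-sided 5% rejection rate = Φ(δ/SE − 1.96) + Φ(−δ/SE − 1.96)

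| Assumed δ (SD) | Rejection rate with no true difference at diagnosis |
|---|---|
| 0.02 | 7% |
| 0.05 | 16% |
| 0.10 | 49% |
| 0.20 | 97% |

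Nothing in the documents says which row applies, or whether δ differs from 0 at all.

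**The case against.** **The phrase may have meant nearest after the test.** Read with its label, the footnote can bear that meaning. However, the literal sense is latest and section 6.2 uses the phrase that way elsewhere. If nearest was intended, up to 30 sites transcribing from the footnote still need to be told so.

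**The mechanism is not documented.** A reader might infer that inpatients typically contribute values near day 10, after treatment. That needs frequent sampling, long stays and treatment that preceded the sample, and the documents give none of these. The treatment list is undated, so it does not show that therapy came first. This objection stands: the wording *allows* such values, but how many patients are affected is unknown.

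**The groups are matched.** A reader might also infer that the HIV comparison is biased. The documents do not establish this. Section 4.1 matches PLWHIV to HIV-negative patients on age, sex, ethnicity where available, month of diagnosis, and inpatient or outpatient diagnosis. A contrast between inpatients and outpatients is therefore not itself the group contrast. Matching does not rule bias out, for two reasons:
- Section 6.2 allows controls from existing cohort databases, whose sampling schedules may differ.
- Matching inpatients 1:1 and outpatients 1:3 leaves the pooled inpatient shares unequal. If, as an assumption, the inpatient share of cases equals the dashboard hospitalisation share in section 6.1 (436/1,187 = 37%), fully matched controls would be 0.37/(0.37 + 3 × 0.63) = 16% inpatient. Case shares of 20% and 50% give 8% and 25%.

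That imbalance is a separate matter which changing the footnote would not cure.

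**Taking the earliest value is only a partial remedy.** A patient first sampled on day 8 still contributes a day-8 value. That is true, but the rule never does worse than the present one.

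**The endpoint is minor.** It is the last of nine secondary endpoints, collected if available, and absent from the primary composite, its covariates and Table 1. This stands and limits the importance of the point.

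**Conclusion.** The label and the definition of secondary endpoint 9 disagree. Following the footnote as written gives a value other than the one nearest diagnosis whenever a patient has results on more than one day in the window. The discrepancy is between 0 and 10 days per patient, and is zero for anyone with a single result. Neither the matching nor the planned covariates correct it.

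The conclusion rests on the literal reading of the footnote, which is the better-supported one but not the only possible one. That the value carries disease course and treatment is plausible, chiefly for inpatients with repeated samples, but it is an inference. The documents support no statement that the HIV comparison is biased, in which direction, or by how much in marker units. The primary endpoint and its analysis are untouched. The point is worth correcting because the better rule is clear and costs little.

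**What to change.** Change footnote 1 to the earliest available value on or after the positive PCR within the same 10-day window. No patient who has a value under the present rule loses it.

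The cost is more than an edit to the footnote. Values already transcribed under the present rule must be rechecked wherever a patient had more than one result.

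Where the sample date is available, record it. This needs one extra eCRF field, which may be missing for controls taken from cohort databases. Use the sampling day in a sensitivity analysis only. It should not be a routine covariate, because the day of sampling may itself follow from severity, which section 3 hypothesises to depend on HIV status. Adjusting for it could remove part of the difference being studied.

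If a data source cannot supply the earliest value, relabel the endpoint as the latest value within 10 days after the positive test, in sections 3.4, 6.2 and 7.3.3 and in the synopsis.

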Study Population & Planned Sample Size	Cases: 500 PLWHIV with COVID-19 Controls: 1,000 PLWHIV without COVID-19 & upto 1500 HIV seronegative COVID-19 patients
Eligibility Criteria	Cases: at least 18 years of age with documented HIV-1 infection and confirmed SARS-CoV-2 infection by documented, or patient-reported, positive result on PCR testing of a nasopharyngeal or respiratory sample, before 1 st April 2021. Controls: at least 18 years of age with either: documented HIV-1 infection; or confirmed SARS-CoV-2 infection by documented, or patient-reported, positive result on PCR testing of a nasopharyngeal or respiratory sample, before 1 st April 2021. Controls must also meet the matching criteria.
Indication	HIV & COVID-19
Methodology	Only real-world retrospective data will be used for this study. Deidentified retrospective data will be transcribed into the eCRF system from source data at each clinical site or from existing COVID-19 cohort databases, where appropriate. No personal identifiable data will be transmitted to NEAT ID. Each case will be matched to control as per the criteria set out below: For comparing PLWHIV & COVID-19 versus HIV seronegative COVID-19 patients, a 1:1 or 1:3 matching will be performed according to the following criteria: 
• Age (+/- 5 years)• Sex• Ethnicity (where available)• Month of COVID-19 diagnosis (+/- 2 months)• COVID-19 diagnosis inpatient, 1:1 matching OR• COVID-19 diagnosis outpatient (ambulatory), 1:3 matching For comparing PLWHIV & COVID-19 versus PLWHIV without COVID-19, a 1:2 matching for similar risk of acquiring COVID-19 will be performed according to the following criteria: 
• Age (+/- 5 years)• Sex• Ethnicity (where available)
Number of sites	Up to 30 sites

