3.1 Primary objective

1. To describe outcomes of COVID-19 in PLWHIV in comparison to HIV seronegative COVID-19 controls.
2. To identify risk factors (e.g. CD4 cell nadir, current CD4 count, co-morbidities) for severe COVID-19 outcomes within the group of PLWHIV.

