4.1 Study Schema

[figure not shown]

Figure 1: Study design with cases (PLWHIV & COVID-19) and two matched control groups.

In total, 500 cases and up to 2500 controls will be analysed.

Only real-world retrospective data will be used for this study. Deidentified retrospective data will be transcribed into the eCRF system from source data at each clinical site or from existing COVID-19 cohort databases, where appropriate.

For comparing PLWHIV & COVID-19 versus HIV seronegative COVID-19 patients, a 1:1 and 1:3 matching will be performed according to the following criteria:

- Age (+/- 5 years)
- Sex
- Ethnicity (where available)
- Month of COVID-19 diagnosis (+/- 2 months)
- COVID-19 diagnosis inpatient, 1:1 matching
OR
- COVID-19 diagnosis outpatient (ambulatory), 1:3 matching

For comparing PLWHIV & COVID-19 versus PLWHIV without COVID-19, a 1:2 matching for similar risk of acquiring COVID-19 will be performed according to the following criteria:

- Age (+/- 5 years)
- Sex
- Ethnicity (where available)

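### Section 7.1 gives 1,500 HIV-only controls where the design has 1,000, and its 28-parameter allowance is for infection; the severity objective, informed only by the 500 cases, has no sample-size statement

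*Combined protocol and SAP*

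**What the plan says.** Section 7.1 (Sample size calculation) sizes the within-PLWHIV analysis by a rule of thumb for multivariable logistic regression, n = 100 + 50i, where i is the number of independent variables in the final model. It introduces the rule with "For the search for factors associated with SARS-CoV-2 infection in PLWHIV" and concludes: "With 1500 PLWHIV (500 with COVID-19 and 1500 controls without COVID-19), we would be able to study 28 parameters".

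The design figures elsewhere are:

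- Synopsis, study population: "Controls: 1,000 PLWHIV without COVID-19 & upto 1500 HIV seronegative COVID-19 patients".
- Section 4.1: "For comparing PLWHIV & COVID-19 versus PLWHIV without COVID-19, a 1:2 matching for similar risk of acquiring COVID-19 will be performed".
- Section 4.1, overall total: "In total, 500 cases and up to 2500 controls will be analysed".

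On the question to be answered, section 3.1 (objective 2) seeks risk factors "for severe COVID-19 outcomes within the group of PLWHIV". The second hypothesis in section 7.3 is also about severe disease. Section 7.3.2 says of the second primary analysis: "The endpoint is to assess factors associated with severe COVID-19 within the group of PLWHIV". The comparison named there, however, is PLWHIV with COVID-19 against PLWHIV without it, by conditional logistic regression. Section 7.3 describes that same model as being for factors associated with COVID-19.

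**The concern.** There are two separate faults.

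First, the sample-size sentence contradicts itself and the rest of the protocol on how many HIV-only controls are planned. This is current text in the section that a reader consults for planned numbers.

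Second, the only sample-size statement about PLWHIV concerns who became infected, whereas the primary objective concerns who became severely ill. Section 5.1 requires HIV-only controls to show no sign of SARS-CoV-2 infection, so they carry no information on severity once infected. If the severity question is answered, it is answered by the 500 cases, and the plan does not say how large a model they can support. The candidate list in section 7.3.2 is long, and the only selection step is a univariable screen at P < 0.20 with no upper limit on model size. An overfitted model for a primary objective is therefore possible, and nothing in the plan guards against it.

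**Working it through.** **Inputs**

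- Rule: n = 100 + 50i, so i = (n − 100)/50 (section 7.1).
- Total PLWHIV stated: 1,500; split stated: 500 and 1,500 (section 7.1).
- HIV-only controls planned: 1,000 (synopsis); matching 1:2 (section 4.1).
- All controls: up to 2,500 (section 4.1); HIV-seronegative controls: up to 1,500 (synopsis).

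**1. Reproducing the plan's figure**

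(1,500 − 100)/50 = 28, an exact match. In reverse, 100 + 50 × 28 = 1,500.

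**2. Which number in the sentence is wrong**

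| Check | Result |
|---|---|
| Split as printed | 500 + 1,500 = 2,000, not 1,500 |
| Rule at n = 2,000 | (2,000 − 100)/50 = 38, not 28 |
| 1:2 matching | 500 × 2 = 1,000 |
| All controls | 1,000 + 1,500 = 2,500, as in section 4.1 |
| Split with 1,000 controls | 500 + 1,000 = 1,500, and the rule gives 28 |

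Every check agrees with 1,000. Only the printed count of 1,500 controls fails.

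**3. The same rule for severity among the cases**

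(500 − 100)/50 = 8.

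**4. How long the candidate list is**

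Section 7.3.2 names age, sex and obesity (3), the Appendix 1 comorbidities (18 rows) and eight HIV-related variables: time since diagnosis, ART, CDC stage, CD4 nadir, last CD4 count, HIV-RNA, CD4% and CD4/CD8 ratio. That is 3 + 18 + 8 = 29 candidates before screening. Parameters outnumber variables, since the five age bands alone use four.

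**5. Expected events among 500 cases (illustration)**

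The documents give no rate for the composite endpoint in PLWHIV. I therefore take single-component rates as an assumed range: deaths on the NEAT ID dashboard, 78/1,187 = 6.6% (section 6.1), and the HIV-negative rates of 11% for death and 15% for ICU (section 7.1).

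| Assumed rate | Events in 500 | Per parameter at 28 | Per parameter at 8 |
|---|---|---|---|
| 6.6% | 33 | 1.2 | 4.1 |
| 11% | 55 | 2.0 | 6.9 |
| 15% | 75 | 2.7 | 9.4 |

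The composite could produce more events than any single component, so these figures may be low. They show that even 8 is not automatically comfortable, because the rule uses total n and ignores the number of events.

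**The case against.** The case for leaving the text largely alone has some force.

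- *The misprint changes no result.* This is right. The total of 1,500 and the 28 are both correct, and the next sentence of section 7.1 repeats 1,500 as the sample size. A reader might infer that sites would recruit 1,500 HIV-only controls. The documents do not support that: selection follows the synopsis number and the matching ratio in sections 4.1 and 5.1. It is still a wrong planned number in the sample-size section and should be corrected.
- *The plan never applies 28 to severity.* This is also right. A reader might infer that it does, because section 7.1 offers no other allowance for the second primary analysis, but the sentence is expressly about infection. For the infected-versus-uninfected comparison, which uses all 1,500, the 28 is consistent. What remains is a gap: objective 2 has no sample-size justification. The gap is made harder to see because section 7.3.2 attaches a severity endpoint to an infected-versus-uninfected comparison.
- *The allowance does not govern the model.* This stands. Section 7.3.2 selects by P < 0.20 and sets no cap, and the rule counts variables in the final model, so 29 candidates cannot be set directly against 28 or 8.
- *Eight is not a sound cap either.* This stands. The rule disregards events, so 8 is what the plan's own logic yields at n = 500 and not a safe number of terms.

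**Conclusion.** The point holds in two parts.

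1. The control count in section 7.1 is wrong as written: it should read 1,000, an overstatement of 500. The error is confined to that one figure. A possible origin is the amendment recorded in Appendix 2 that raised a different group, the COVID-19-only controls, to 1,500, but that is inference.
2. Primary objective 2 has no sample-size support. The stated 28 belongs to the infection analysis at n = 1,500. For severity the informative sample is 500, and the plan's rule gives at most 8 variables.

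The stronger conclusion, that the plan allots 28 parameters to the severity model and would therefore overfit it, is not established. Overfitting is a risk left open by the absence of any limit. How large that risk is depends on the composite event rate in PLWHIV, which the documents do not give.

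The second part assumes that objective 2 means severity among PLWHIV who have COVID-19. That is the natural reading of sections 3, 3.1 and 7.3.

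**What to change.** - In section 7.1, change the number of controls without COVID-19 from 1500 to 1,000. Leave the total of 1,500 and the 28 as they are.
- State that the 28 applies only to the comparison of PLWHIV with and without COVID-19 (n = 1,500).
- Add a statement for severity among the 500 PLWHIV with COVID-19: the plan's rule gives at most 8 variables, and the final model size will be set against the expected number of composite events, counting parameters so that multi-level factors are not undercounted. State the assumed event rate and a range. Do not fix the model at 8 terms on the strength of the rule alone.
- In section 7.3.2, separate the infection analysis from the severity analysis so that each has its own population and outcome.

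The first two changes are a line each. The last two cost more: the plan does not at present describe a severity model confined to the cases, so one has to be written, and the variable allowance will be less favourable than 28. No additional patients or data items are needed.
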